^M During outpatient treatment, patients will undergo cardio-respiratory monitoring using a specialized ambulatory data acquisition system (BioRadio). In addition, respiratory function will be assessed in the clinic using a similar device (SOMNOtouch).

^N During outpatient treatment, patients will undergo cardio-respiratory monitoring using a specialized ambulatory data acquisition system (BioRadio). Respiratory monitoring will be attempted at home for 6 hours each day during the time awake at Screening (three 3-day periods during the first, second and third week), and on any 3 days in the week preceding each subsequent scheduled office visit. Data recorded using this system will be downloaded from the device at home using the Internet/WiFi or a dedicated laptop provided by the Sponsor, if Internet access is not available; data collected during the screening test period will be verified for accuracy by Vivonoetics.

^O To be performed for all post-pubertal females.

^P MECP2 genetic mutation testing will be performed only if the patient has not had the test performed previously, or does not have adequate documentation of the test results from an accredited laboratory.

Document:	\\ieedc-vnasc01\BIOSdata\Newron\Sarizotan\PXA76395\Biostatistics\Documentation\SAP		
Author:	[name]	Version Number:	V2
		Version Date:	[30March2020]

Template No: CS_TP_BS016 – Revision 4
Effective Date: 01Apr2016

Reference: CS_WI_BS005

3.3. CHANGES TO ANALYSIS FROM PROTOCOL

None.

4. PLANNED ANALYSES

One analysis is planned for the 24-week, double-blind treatment period, and a separate analysis will be performed for the open-label extension period, once it is completed. The analysis of the data from the open-label period will be described in a separate SAP. The analysis for PK parameters and analysis for ECG data will also be described in separate SAPs.

4.1. INTERIM ANALYSIS

No interim analysis was planned for this study.

4.2. FINAL ANALYSIS

All final, planned analyses identified in this SAP will be performed by IQVIA Biostatistics team following Sponsor authorization of this SAP and Database Lock.

5. ANALYSIS POPULATIONS AND STUDY PERIOD

Subjects to be included/excluded from each analysis population set will be determined before unblinding

5.1. ITT POPULATION

The Intent-to-Treat (ITT) population will include all patients who were randomized to treatment.,.

This population will be used for all efficacy analyses.

5.2. PER PROTOCOL POPULATION

The Per Protocol population will include all patients in the ITT population who also meet the

Document:	\\ieedc-vnasc01\BIOSdata\Newron\Sarizotan\PXA76395\Biostatistics\Documentation\SAP	Version Number:	V2
Author:	[name]	Version Date:	[30March2020]
Template No:	CS_TP_BS016 – Revision 4	Reference:	CS_WI_BS005
Effective Date:	01Apr2016		

following criteria:

- Have no critical protocol deviations during the study, including meeting critical study entry criteria.
- Have been compliant with study medication administration, as evident from a “Yes” response to the CRF question “Was the IP taken Per Protocol (PP) (two times a day)?” on the drug accountability form at the Week 24 (final) visit. In patients with a “No” response, a further review of the compliance data at Week 24 was performed to identify those to be excluded from the Per Protocol population.
- Have no major efficacy data missing.

Patients who meet the above criteria will be identified prior to database lock and unblinding.

This population will be used for supportive efficacy analyses.

5.3. SAFETY POPULATION

The Safety population will include all patients who took at least one dose of study medication. The safety analyses are based on the actual treatment received.

This population will be used for all safety analyses.

5.4. 24-WEEK DOUBLE-BLIND TREATMENT PERIOD

The 24-week, double-blind, treatment period included all patients who provided informed consent, or the patient’s parent, legal guardian, or representative provided written informed consent, prior to the patient’s participation in the trial, met all of the selection criteria, including diagnostic and respiratory criteria, for enrolment in the study, and were randomized to treatment.

5.5. INITIAL 24-WEEK OPEN-LABEL EXTENSION TREATMENT PERIOD

Patients were eligible for the 24-week Initial open-label treatment period if they completed the final evaluations at Week 24 (Day 168), and met the following criteria:

1. Had no safety or tolerability issues that would have precluded continuing the study medication.
2. Had been compliant with the trial requirements.
3. Had not worsened to the extent that they were considered at an increased risk for

Document:	\\ieedc-vnasc01\BIOSdata\Newron\Sarizotan\PXA76395\Biostatistics\Documentation\SAP		
Author:	[name]	Version Number:	V2
		Version Date:	[30March2020]
Template No:	CS_TP_BS016 – Revision 4	Reference:	CS_WI_BS005
Effective Date:	01Apr2016		

morbidity or mortality, as judged by the Investigator.

5.6. THREE ADDITIONAL 48-WEEK OPEN-LABEL EXTENSION TREATMENT PERIODS

Three additional 48-week open-label treatment periods were added to the study and will include all patients who provided informed consent at Weeks 48, 96 and 144, and for whom the investigators believe the patients are benefitting from treatment with sarizotan and are not experiencing any significant adverse events.

6. GENERAL CONSIDERATIONS

Descriptive statistics for continuous variables will be summarized by treatment group with n, mean, standard deviation (SD), median, minimum, and maximum, where appropriate. Descriptive statistics for categorical variables will be summarized by treatment group with count and percentages. All percentages should use the total number of subjects with data available in the relevant analysis set as the denominator, unless otherwise specified. Categories for missing data will be presented as appropriate.

Decimal places format

In general, the number of decimal places displayed for each statistic will be determined as follows, unless otherwise specified:

Descriptive Summaries	
Range (Min, Max)	Recorded decimal places
Mean, Median, Geometric Mean	Recorded decimal places + 1
Standard Deviation, Standard Error	Recorded decimal places + 2
Inferential Statistics	
LS Means, Difference in LS Means	Recorded decimal places + 1
CI's corresponding to LS Means and Difference in LS Means	Recorded decimal places + 2
Odds Ratio	Recorded decimal places + 3
Listings	Recorded decimal places

Percentages: All percentages between 0 and 99 will be rounded to one decimal unless there is a need to report more than one decimal for percentages (e.g., AEs).

P-values, if any, shall be reported to four decimal places or as <0.0001.

Data from subjects excluded from an analysis set will be included in the data listings, but not in the summaries.

Document: \\ieedc-vnasc01\BIOSdata\Newron\Sarizotan\PXA76395\Biostatistics\Documentation\SAP
 Author: [name] Version Number: V2
 Version Date: [30March2020]

Template No: CS_TP_BS016 – Revision 4
 Effective Date: 01Apr2016

Reference: CS_WI_BS005

6.1. REFERENCE START DATE AND STUDY DAY

Study Day will be calculated from the reference start date, and will be used to show start/stop day of assessments and events.

Reference start date is defined as the day of the first dose of study medication (Day 1 is the day of the first dose of study medication), and will appear in every listing where an assessment date or event date appears.

If the date of the event is on or after the reference start date then:

Study Day = (date of event – reference start date) + 1.

If the date of the event is prior to the reference start date then:

Study Day = (date of event – reference start date).

In the situation where the event date is partial or missing, the date will appear partial or missing in the listings, and Study Day, and any corresponding durations will be presented based on the imputations specified in Appendix 1; Partial Date Conventions.

6.2. BASELINE

Unless otherwise specified, baseline is defined as the last non-missing measurement taken prior to reference start date (including unscheduled assessments). In the case where the last non-missing measurement and the reference start date coincide, that measurement will be considered pre-baseline, but Adverse Events (AEs) and medications commencing on the reference start date will be considered post-baseline.

6.3. RETESTS, UNSCHEDULED VISITS AND EARLY TERMINATION DATA

In general, for by-visit summaries, data will be reported by the protocol-defined nominal visit. For each nominal visit a pre-specified analysis window has been defined (Section 8). These analysis windows will define the visit at which the data are reported. Listings will include scheduled, unscheduled, retest and early discontinuation data.

6.4. STATISTICAL TESTS

All statistical tests of treatment effects will be conducted to compare sarizotan (high dose group and low dose group) versus placebo at a two-sided alpha level of 0.05, unless otherwise specified.

Document:	\\ieedc-vnasc01\BIOSdata\Newron\Sarizotan\PXA76395\Biostatistics\Documentation\SAP		
Author:	[name]	Version Number:	V2
		Version Date:	[30March2020]
Template No:	CS_TP_BS016 – Revision 4	Reference:	CS_WI_BS005
Effective Date:	01Apr2016		

6.5. COMMON CALCULATIONS

For quantitative measurements, change from baseline at Visit X will be calculated as:

$$\text{Value at Post-baseline Visit X} - \text{Baseline Value}$$

For quantitative measurements, percentage change from baseline at Visit X will be calculated as:

$$((\text{Value at Post-baseline Visit X} - \text{Baseline Value}) / \text{Baseline value}) * 100$$

Age will be calculated as following:

$$\text{Age} = (\text{Date of informed consent} - \text{Date of Birth} + 1) / 365.25$$

6.6. SOFTWARE VERSION

All analyses will be conducted using SAS Enterprise Guide 7.13 (64-bit).

7. STATISTICAL CONSIDERATIONS

7.1. ADJUSTMENTS FOR COVARIATES AND FACTORS TO BE INCLUDED IN ANALYSES

Baseline value and age will be adjusted as covariates, and treatment as fixed factor will be included in the analyses wherever applicable.

7.2. MULTICENTER STUDIES

This study will be conducted by multiple investigators at multiple centers. Randomization to treatment arms was not stratified by country/ center. Centers will be grouped in regions for purposes of the analyses as follows:

- Europe (United Kingdom and Italy)
- India
- US and Australia.

Document:	\\ieedc-vnasc01\BIOSdata\Newron\Sarizotan\PXA76395\Biostatistics\Documentation\SAP		
Author:	[name]	Version Number:	V2
		Version Date:	[30March2020]

Template No: CS_TP_BS016 – Revision 4
 Effective Date: 01Apr2016

Reference: CS_WI_BS005

7.3. MISSING DATA

All data obtained for the ITT population will be used in the analysis. Missing efficacy data for the primary endpoint will not be imputed. Last observation carried forward (LOCF) method will be adopted as imputation for the secondary quantitative endpoints (wherever required). Details of which endpoint will be imputed using LOCF approach can be found in the respective endpoint's section description.

7.4. MULTIPLE COMPARISONS/ MULTIPLICITY

The study level error rate will be controlled by following a sequential multiple testing procedure, where testing will begin with the primary efficacy endpoint. The effects of the high dose sarizotan versus placebo will be analyzed first for all parameters in a pre-specified sequence.

The sequence of testing will be as presented below:

- Percentage reduction (change) from baseline in the number of apnea episodes,
- Mean rating of CIC
- Mean change from baseline in the Top Three Concerns Total Score.

7.5. EXAMINATION OF SUBGROUPS

Subgroup analyses will be performed for patients dichotomized by age groups of less than 13 years of age, and 13 years of age and older.. No inferential statistics will be performed for these sub-groups.

8. OUTPUT PRESENTATIONS

In tables, the order and naming of the treatment groups will be as follows:

- Sarizotan Low Dose
- Sarizotan High Dose
- Placebo

In addition to the above treatment groups, the outputs will also be presented for Sarizotan threshold plasma concentration for the primary efficacy and demographics as follows

- Sarizotan (>400 ng/ml)
- Placebo

Document:	\\ieedc-vnasc01\BIOSdata\Newron\Sarizotan\PXA76395\Biostatistics\Documentation\SAP		
Author:	[name]	Version Number:	V2
		Version Date:	[30March2020]
Template No:	CS_TP_BS016 – Revision 4	Reference:	CS_WI_BS005
Effective Date:	01Apr2016		

In addition to above treatment groups, the outputs will also be presented for Sarizotan pooled dose as follows:

- Sarizotan (all doses)
- Placebo

In listings, the order and naming of the treatment groups will be as follows:

- Sarizotan Low 2 mg dose
- Sarizotan Low 5 mg dose
- Sarizotan High 5 mg dose
- Sarizotan High 10 mg dose

Placebo

For visit presentations, the naming of the visit will be as follows:

Screening
Day 0 (Baseline)
Day 1
Day 2
Day 7
Day 14
Day 15
Week 8
Week 16
Week 24
Safety Follow-up

Document: \\ieedc-vnasc01\BIOSdata\Newron\Sarizotan\PXA76395\Biostatistics\Documentation\SAP
 Author: [name] Version Number: V2
 Version Date: [30March2020]

Template No: CS_TP_BS016 – Revision 4 Reference: CS_WI_BS005
 Effective Date: 01Apr2016

8.1. DATA SELECTION FOR DOUBLE BLIND TREATMENT PERIOD (24 WEEKS)

For patients who enter the open-label extension treatment period, all data up to and including the date of the first dose in the open-label extension phase will be considered as part of the double-blind treatment period (24 weeks). For patients who do not enter the open-label extension, all data will be included in the double-blind treatment period (24 weeks).

8.2. VISIT WINDOWS:

The following visit windows will be used for analyses of efficacy endpoints:

Visit	Window
Screening (day - 28)	Day - ∞ to day -1
Baseline (day 0)	Day -28 to day 0 (last value before first dose of study drug) [Baseline for the BioRadio™ data will be the last value prior to Day 1 (no cutoff at Day -28)]
Day 1	No window (day of the first dose taken)
Day 2	No window (immediately after day 1)
Week 2 (day 14)	Day 1 to day 35
Day 15	No window (immediately after day 14)
Week 8 (day 56)	Day 36 to day 84
Week 16 (day 112)	Day 85 to day 140
Week 24 (day 168)	Day 141 to day 196
Safety follow - up	Day 1 – Day 30 where Day 0 Is the day when the patient discontinues the study. This Is likely to be a scheduled visit day – but possibly an unscheduled visit. Operationally it might be identified by being the previous day that a vital sign was measured (or any other measurement that is done when a patient either reaches Week 24 or discontinues prematurely – as per the protocol schedule of evaluations). Importantly the patient is no longer on drug during this entire window.

Note: Day 1 = first dosing day of study drug

Document:	\\iecdc-vnasc01\BIOSdata\Newron\Sarizotan\PXA76395\Biostatistics\Documentation\SAP	Version Number:	V2
Author:	[name]	Version Date:	[30March2020]

Template No: CS_TP_BS016 – Revision 4
 Effective Date: 01Apr2016

Reference: CS_WI_BS005

If there is more than one record within the same window, the non-missing value closest to the scheduled visit study day will be used for analyses. If two values are equidistant from the scheduled visit day, the earliest non-missing value will be used.

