All patients, including those randomized to placebo, who have completed the final evaluations at Week 24 (Day 168), have no safety or tolerability issues that would preclude continuing on the study medication, have been compliant with the trial requirements, and have not worsened to the extent that they are considered at an increased risk for morbidity or mortality, as judged by the Investigator, will have the option of continuing open-label treatment with sarizotan for 24 weeks. Each patient's parent, legal guardian, or representative, must provide written informed consent prior to the patient's participation in this initial

Amend. 1, 19Jan2016; Amend. 2, 18May2016; Amend. 3, 21Oct2016; Amend. 4, 03Mar2017; Amend. 5, 29Mar2017; Amend. 6, 13Apr2017; Amend. 7, 02Oct2017; Amend. 8, 02Nov2017; Amend. 9, 11Feb2018; Amend. 10, 29Nov2018; Amend. 13, 10Dec2019; Amendment 14, 17 March 2020, Clean, Final

extension period. The patient should provide assent, if capable of doing so. At the end of the initial 24 weeks of open-label treatment, the Investigator will make a global assessment of the patient. If in the Investigator's opinion, the patient is benefitting from treatment with sarizotan and is not experiencing any significant adverse events, they will be eligible to continue open-label treatment. Informed consent must be obtained at Week 48, for the patient to continue open-label treatment for an additional 48 weeks (through Week 96), again at Week 96 for the patient to continue open-label treatment for another 48 weeks (through Week 144), and again at Week 144 for the patient to continue open-label treatment for another 48 weeks (through Week 192).

At Week 24 (Day 168), all patients ≥ 13 years of age and weighing ≥ 25 kg, including those originally randomized to placebo and those receiving 5 mg once daily, will receive treatment with sarizotan, and will start at a dose of 5 mg *bid*. Patients 4 to < 13 years of age and patients ≥ 13 years of age but weighing < 25 kg, including those who were randomized to placebo, will receive sarizotan at a starting dose of 2 mg *bid*. If patients do not tolerate this starting dose, the Investigator will instruct the caregiver to administer only the morning dose (i.e. 2 or 5 mg once daily) for a few days prior to reinitiating the intended *bid* dose (i.e. 2 or 5 mg *bid*). If the 2 or 5 mg *bid* dose is still not tolerated, a reduction to 2 or 5 mg once daily will be permitted.

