At Week 28 (Day 196), patients ≥ 13 years of age and weighing ≥ 25 kg will have their dose increased to 10 mg *bid*, if the starting dose was well tolerated, or may remain on a lower dose. Patients 4 to < 13 years of age and weighing 10 to < 18 kg will remain on a dose of 2 mg *bid*, while those weighing ≥ 18 kg, as well as patients ≥ 13 years of age but weighing < 25 kg, will have their dose increased to 5 mg *bid*, provided there are no tolerability issues. If the patient does not tolerate the target dose (2, 5 or 10 mg *bid*, based on age and weight criteria, the Investigator will instruct the caregiver to administer only the morning dose (i.e. 2, 5 or 10 mg/day) for a few days prior to reinitiating the intended *bid* dose (i.e. 2, 5 or 10 mg *bid*). If the target dose of 2, 5 or 10 mg *bid* is still not tolerated, a reduction to 2 mg once daily, 2 mg *bid* or 5 mg *bid*, respectively, will be permitted. Patients will continue on their maximum tolerated dose (MTD) through the final dose, unless intolerance develops, and a dose reduction is warranted.

The final evaluations performed at Week 24 in the double-blind period, including assessments of respiratory function performed in the clinic using a stretch-sensitive resistance plethysmograph (SOMNOtouch), vital signs (body weight, height, temperature, respiratory rate, pulse, and systolic and diastolic blood pressure), laboratory tests (hematology, biochemistry, urinalysis, serum prolactin, plasma ACTH and cortisol, serum pregnancy test for post-pubertal females), ECG, physical and neurological examinations, Tanner Staging, routine ophthalmological examination [including Optical Coherence Tomography (OCT), if feasible] and final assessments for other efficacy variables [Motor-Behavioral Assessment Scale, Caregiver Top 3 Concerns, and Rett syndrome Clinical Severity Scale (RCSS)] will serve as the baseline assessments for the open-label extension period. Once all of these Week 24 assessments have been completed, and the consent form for the extension period has been signed, patients meeting all entry criteria will start on the low dose (5 mg *bid*) of sarizotan.

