The first dose of the extension period (2 or 5 mg sarizotan) should be administered in the clinic (if the morning dose was given, wait at least 6 hours after the prior dose before administration) on the same day (Day 168); however, if necessary, it can be postponed until the following morning. Patients will be observed for the occurrence of any adverse events in the initial 4-hour period after the first dose. Safety evaluations (vital signs, 12-lead ECG, physical and neurological examinations) will be performed at 1 and 4 hr- post-dose. If no significant side effects are noted within the 4-hr period following the first dose, the patient will be released from the hospital and given a supply of study medication for the remainder of the first four weeks of dosing at 2 or 5 mg *bid*.

The patient/caregiver will receive a telephone contact from the Investigator/site staff on Day 175 (Week 25) to inquire about the tolerability of the current dose of the study medication. If there are no tolerability

Amend. 1, 19Jan2016; Amend. 2, 18May2016; Amend. 3, 21Oct2016; Amend. 4, 03Mar2017; Amend. 5, 29Mar2017; Amend. 6, 13Apr2017; Amend. 7, 02Oct2017; Amend. 8, 02Nov2017; Amend. 9, 11Feb2018; Amend. 10, 29Nov2018; Amend. 13, 10Dec2019; Amendment 14, 17 March 2020, Clean, Final

issues, the patient/caregiver will be instructed to continue on the current dose. If intolerance develops, a reduction to 2 or 5 mg once daily can be instituted, or if necessary, the patient can be asked to return to the clinic for an unscheduled visit for a full assessment.

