An Unexpected Adverse Drug Reaction is adverse event, the nature or severity of which is not consistent with the applicable product information (e.g., Investigator's Brochure for an unapproved investigational product or package insert/summary of product characteristics for an approved product).

Non-Serious Adverse Event

A non-serious adverse event is any adverse event that does not meet the criteria listed above for a serious adverse event.

Treatment-Emergent Adverse Events

Adverse events that are newly occurring or worsened in severity after administration of the study medication are considered to be treatment-emergent AEs (TEAEs). In the open-label extension period, only newly occurring AEs and AEs that were ongoing at Week 24 and worsen in severity will be considered TEAEs.

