15.2.4 Concomitant therapy

A listing of concomitant medications administered from the time of the first dose of the study medication through completion of the final (Week 192) evaluations will be summarized by treatment group for the double-blind period (Days 1-168), and overall for the open-label extension period (Days 169-1344).

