15.2.5 Safety evaluations

All subjects who receive a dose of study medication will be included in the safety analyses. All adverse events will be listed and summarized by body system and preferred term. The incidence of AEs (%) and their relatedness to the study drug, as assessed by the Investigator, will be reported. Serious adverse events (SAEs) and events which are newly occurring or worsening after administration of the study medication (TEAEs) will be summarized. In addition, adverse events that result in death or discontinuation (ADOs) of the study medication will be listed separately.

Results for other safety parameters such as vital signs, laboratory parameters, ECGs, physical, neurological and ophthalmological examinations, and the suicidality assessment, will be listed and summarized accordingly. Changes from baseline in vital signs, ECG and laboratory values, and physical, neurological and ophthalmological examination findings will be summarized, with abnormal and clinically notable values/findings being identified. In the initial 24-week, double-blind, placebo-controlled period, a comparison will be made between the sarizotan and placebo groups in the proportion of subjects experiencing SAEs, ADOs, and TEAEs and any clinically significant abnormalities in other safety parameters. Where feasible, mean changes from baseline will be examined using a paired t-test. Safety data for the open-label extension period will be analyzed separately and will use the Week 24 evaluations from the double-blind period as the baseline assessments.

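### SAP 8.1 ends the double-blind period by calendar date, so adverse events after a former placebo patient's first sarizotan dose that day count as double-blind placebo events

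*SAP*

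**What the plan says.** SAP 8.1 defines the double-blind data of a patient who enters the extension as "all data up to and including the date of the first dose in the open-label extension phase". It makes no exception for adverse events.

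Protocol 11.2 describes what happens on that date. Patients under 13, and older patients under 25 kg, "including those who were randomized to placebo, will receive sarizotan at a starting dose of 2 mg" twice daily; the older, heavier patients, again including former placebo patients, start on 5 mg twice daily. Dosing begins "Once all of these Week 24 assessments have been completed" and extension consent is signed, on Day 168 if possible; "however, if necessary, it can be postponed until the following morning". After the dose, "Patients will be observed for the occurrence of any adverse events in the initial 4-hour period after the first dose".

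SAP 17.1 and the algorithm in SAP Appendix 1 classify an event as treatment-emergent by comparing its start with the original start of study medication. The algorithm uses dates only. SAP 17.1.1 gives the adverse event overview by period, and SAP 8 sets the table columns as Low Dose, High Dose and Placebo.

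The protocol treats the extension separately. Section 15.2.5 states that "Safety data for the open-label extension period will be analyzed separately", and section 13.1.1 says that in the extension "only newly occurring AEs and AEs that were ongoing at Week 24 and worsen in severity will be considered TEAEs". Section 15.2.4 sets a day boundary, for concomitant therapy only: Days 1-168 are double-blind and Days 169-1344 are extension.

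**The concern.** A former placebo patient takes sarizotan for the first time on a date that SAP 8.1 places wholly in the double-blind period. Any reaction later that day is then reported as a placebo event. First-day events are plausible: Protocol 7.1.3 reports peak concentration within one hour and names dizziness, headache and somnolence as the most frequent Phase I nervous-system events. The protocol also actively looks for events in the hours after the dose.

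The misassignment is largely one-sided. Sarizotan patients entering the extension have had 24 weeks of drug, and those at their target dose restart at the same dose or a lower one. Events moved into the placebo column therefore raise the placebo rate and shrink the apparent excess on drug. Protocol 15.2.5 plans a double-blind comparison of the proportions with serious events, events leading to discontinuation and treatment-emergent events. Understating a difference there is the less cautious direction, in a population with no previous paediatric or Rett syndrome exposure (Protocol 7.3).

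**Working it through.** The documents state no figure on this point, so there is none to reproduce. The check has two parts.

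**1. Applying the rules to test onset times.** Suppose the first open-label dose is given at 13:00.

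| Onset of event | Treatment-emergent (SAP Appendix 1) | Period under SAP 8.1 | Period under a date-time cut |
|---|---|---|---|
| 09:00, same day | yes | double-blind | double-blind |
| 14:00, same day | yes | double-blind | extension |
| 23:59, same day | yes | double-blind | extension |
| 00:01, next day | yes | extension | extension |

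The two rules differ exactly for events after the dose on that date. If the dose is postponed to the next morning, the same problem moves to that date.

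No other rule resolves it:

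- SAP 5.3 bases safety analyses on treatment actually received, but does not say how to split one patient's events at the switch.
- The SAP 8.2 windows are stated for efficacy endpoints.
- Protocol 13.1.1 and 15.2.5 separate the extension without a clock-time start.
- The day split in Protocol 15.2.4 agrees with SAP 8.1 for a first open-label dose on Day 168 and differs for one on Day 169.

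**2. Illustrative size.** Inputs from Protocol 15.2.8: 43 patients per arm, of whom 34 complete. Assumed, because the documents are silent: the first-day event rate *q*, the share *s* of completers who enter the extension, and the share *p* who already had a treatment-emergent event.

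- Patients moved into the placebo count = 34 × *s* × *q*
- Shift in percentage points = 100 × 34 × *s* × *q* / 43
- Shift in the any-event row = that value × (1 − *p*), since a patient with an earlier event is already counted

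| *q* | *s* = 1: patients (points) | *s* = 0.75: patients (points) | Any-event row, *s* = 1, *p* = 60% | Any-event row, *s* = 1, *p* = 90% |
|---|---|---|---|---|
| 2% | 0.7 (1.6) | 0.5 (1.2) | 0.6 points | 0.2 points |
| 5% | 1.7 (4.0) | 1.3 (3.0) | 1.6 points | 0.4 points |
| 10% | 3.4 (7.9) | 2.6 (5.9) | 3.2 points | 0.8 points |
| 20% | 6.8 (15.8) | 5.1 (11.9) | 6.3 points | 1.6 points |

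For example, at *q* = 10% and *s* = 1: 34 × 0.10 = 3.4 patients; 3.4 / 43 = 7.9 points; 7.9 × 0.40 = 3.2 points. A row for a single preferred term can move by up to the unadjusted amount if all the first-day events fall under that term and those patients had not reported it before.

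**The case against.** The strongest reply is that the misassignment is one literal reading. SAP 5.3, with Protocol 13.1.1 and 15.2.5, points the other way, and a sensible programmer might keep a post-sarizotan event out of the placebo column. Table templates and an open-label SAP also exist or are planned, and neither is available here. Those sections do show the intent, but none sets an event-level or clock-time rule, while SAP 8.1 is explicit. Unseen documents cannot be assumed to correct it. If the open-label SAP starts on the same date, these events could be counted twice.

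Whole-day cuts are also this SAP's usual convention, and the inclusive date sensibly keeps the Week 24 assessments in the double-blind period. That stands, and any fix must preserve it.

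The objection on size also largely stands. Protocol 7.1.4 reports no tolerability findings in the Parkinson's disease studies up to 10 mg twice daily, and SAP 1 reports no signs of intolerance in emerging data from this trial. Nothing in the documents supports the 10% and 20% rows. At 2% to 5%, with 60% to 90% already having an event, the any-event row moves by only 0.2 to 1.6 points. The SAP plans no formal test of adverse events, and listings showing study day would let a careful reader find such cases.

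Two narrower objections have force. The days in Protocol 15.2.4 are nominal and the Week 24 visit has a window of ±7 days, so that comparison carries limited weight. The 1-hour and 4-hour post-dose readings are scheduled under the extension baseline visit (Protocol 11.4.12), and reporting by nominal visit (SAP 6.3) may already keep them out of the double-blind summaries.

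**Conclusion.** The concern holds. On its wording, SAP 8.1 attributes to placebo any event that starts after a former placebo patient's first sarizotan dose on that date, and no other provision reassigns it. Any first-day drug events would bias the double-blind safety comparison towards a smaller drug-placebo difference.

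The size is unknown. The upper bounds of 1.6 to 15.8 points assume that all 34 completers switch and that first-day rates lie between 2% and 20%; the documents' tolerability statements make the low end more credible.

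The effect is confined to one calendar date per switching patient and to descriptive safety tables. The Week 24 efficacy assessments precede the dose, and ECG has its own SAP. The point is modest but should be corrected, because the data needed to classify these events are already collected.

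**What to change.** Amend SAP 8.1 so that, for safety data, the double-blind period ends at the date and time of the first open-label dose:

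- Keep the pre-dose Week 24 assessments in the double-blind period.
- Assign events with onset at or after that time, and the 1-hour and 4-hour post-dose assessments, to the extension.
- State a rule for same-day events with no recorded onset time, and report how many there are.
- Use the same boundary in the open-label SAP, and reconcile it with Protocol 13.1.1, 15.2.4 and 15.2.5, so that no event is counted twice or lost.

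As a clarification only, SAP 17.5 could state that notable vital signs at Week 24 use pre-dose readings. SAP 6.3 and the earliest-value rule in SAP 8.2 probably give this already, although 8.2 is introduced as applying to efficacy endpoints.

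The cost is SAP wording and programming. Event onset time (Protocol 13.1.2) and the clock time of the first open-label dose (Protocol 10.2) are already recorded, and no trial procedure changes.
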